## 14.0 Body Fluid Biospecimens: None

## 15.0 Drug Information

The literature reports no deleterious effect was revealed in toxicity testing of  $^{18}\text{F}$ -DOPA-PET, and concludes the toxicological safety of the product is guaranteed given the toxicity data of the various potential impurities.  $^{18}\text{F}$ -DOPA-PET is currently in production at these institutions, and is used to image Parkinson's patients to study the  $^{18}\text{F}$ -DOPA uptake in the caudate nucleus and putamen.

## 16.0 Statistical Considerations and Methodology

### 16.1 Study Overview

This protocol will assess the overall survival of newly diagnosed elderly glioblastoma patients using a one-stage phase II study design.

16.1.1 Primary endpoint: The primary endpoint of this trial is the proportion of patients alive (overall survival) at 12 months based on our hypothesis that the combination of more accurate delineation of high density tumor by  $^{18}\text{F}$ -DOPA-PET combined with hypofractionated proton therapy will improve overall tumor control. All patients meeting eligibility criteria who have signed a consent form and who have begun treatment will be evaluable for the endpoint.

### 16.2 Statistical Design

A patients will be considered a success if they are alive at 12 months. Previous studies and institutional data indicate a median overall survival between 6 and 9 months, therefore we estimate median overall survival (OS) to be 7.5 months, which corresponds to 33% of patients surviving at 12 months. Therefore the largest success proportion where the proposed treatment regimen would be considered ineffective in this population is 33%, and the smallest success proportion that would warrant subsequent studies with the proposed regimen would be 50% (corresponding to a median OS of 12 months). The following single stage one-sided Exact test for proportions design uses 39 evaluable patients to test the null hypothesis that the proportion of successes is at most 33% with an overall significance level (alpha) of 0.1, and a power of 82% to detect a true success proportion of 50%.

#### 16.2.1 Decision Rules

16.2.1.1 If 17 or fewer successes are observed in the first 39 evaluable patients that have been followed for at least 12 months, we will consider this regimen to be ineffective in this patient population. If 18 or more successes are observed in the first 39 evaluable patients, we may recommend further testing of this regimen in subsequent studies in this patient population.

16.2.1.2 Over Accrual: If more than the target number of patients are accrued, the additional patients will not be used to evaluate the stopping rule or used in any decision making process.

#### 16.2.2 Sample Size

The one-stage design to be utilized is fully described in Section 16.22. A minimum of 39 evaluable patients will be accrued to this phase-II study unless undue toxicity is encountered. We anticipate accruing an additional 4 patients to account for ineligibility, cancellation, major treatment violation, or other reasons. Maximum projected accrual is therefore 43 patients.

### 16.2.3 Accrual Time and Study Duration

We anticipate enrolling 15-20 patients per year and thus plan to finish accrual of patients by year 2, leaving year 3 for follow-up and analysis. Therefore, the overall study duration is expected to be 36 months.

### 16.2.4 Power and Significance Levels

Assuming the number of successes is binomially distributed, the significance level is 0.075 and the probability of declaring that this regimen warrants further studies (i.e. statistical power) under various success proportions and the probability of stopping accrual can be tabulated as a function of the true success proportion as shown in the following table.

If the true success proportion is ...	0.35	0.40	0.45	0.50	If the true success proportion is ...
Then the probability of declaring that the regimen warrants further studies is...	0.16	0.37	0.62	0.82	Then the probability of declaring that the regimen warrants further studies is...

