## 16.3 Analysis Plan

The analysis for this trial will commence at the time the patients have become evaluable for the primary endpoint (see 16.2). Such decision will be made by the Statistician and Study chair, in accord with the Cancer Center Statistics (CCS) Standard Operating procedures, availability of data for secondary endpoints, and the level of data maturity. It is anticipated that the earliest date in which the results will be make available via a manuscript, abstract, or presentation format is when 39 patients have been followed for at least 12 months.

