### 16.3.1 Primary Endpoint:

16.3.1.1 Definition: The primary endpoint of this trial is the proportion of alive (overall survival) at 12 months. Survival time is defined as the time from registration to death due to any cause. All patients meeting eligibility criteria who have signed a consent form and who have begun treatment will be evaluable for the endpoint. All eligible patients will be followed until death or a maximum of 5 years.

16.3.1.2 Estimation: The proportion of successes will be estimated by the number of successes divided by the total number of evaluable patients. Confidence intervals for the

true success proportion will be calculated utilizing Exact Binomial methodology. The distribution of survival time will be estimated using the method of Kaplan-Meier (1958).

16.3.1.3 Over Accrual: If more than the target number of patients are accrued, the additional patients will not be used to evaluate the stopping rule or used in any decision making processes; however, they will be included in final point estimates and confidence limits.

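### The primary decision rule (18 or more of 39) has exact power of 74% at a true 50%, not 82%, and attained alpha of 0.060, not 0.075; all four power-table entries are too high

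*Combined protocol and SAP*

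**What the plan says.** Section 16.2 names the test and the sample size: "The following single stage one-sided Exact test for proportions design uses 39 evaluable patients". The null success proportion is 33%, derived from a 7.5-month median, and the alternative is 50%. The design is stated "with an overall significance level (alpha) of 0.1, and a power of 82% to detect a true success proportion of 50" percent.

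Section 16.2.1.1 sets the rule. "If 17 or fewer successes are observed in the first 39 evaluable patients", the regimen is considered ineffective; with 18 or more, further testing may be recommended.

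Section 16.2.4 gives the operating characteristics: "Assuming the number of successes is binomially distributed, the significance level is 0.075". Its table puts the probability of a positive decision at 0.16, 0.37, 0.62 and 0.82 for true proportions of 0.35, 0.40, 0.45 and 0.50.

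Section 16.2.2 allows for four more patients, to a maximum of 43. Section 16.2.1.2 keeps any beyond the target out of the decision: "the additional patients will not be used to evaluate the stopping rule or used in any decision making process". Section 16.3.1.3 repeats this and brings them back for estimation only: "however, they will be included in final point estimates and confidence limits".

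**The concern.** The sample size, cut-off, null, alternative and distribution are all stated, so alpha and power follow with no further assumption. The printed values are not the ones that follow.

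This is the rule that decides the trial. If power is overstated, anyone approving the study, or reading a negative result, will believe a worthwhile regimen is less likely to be missed than it is.

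**Working it through.** **Inputs.** n = 39, null p0 = 0.33, alternative p1 = 0.50, one-sided alpha ceiling 0.1 (Section 16.2); positive decision if X ≥ 18 (Section 16.2.1.1); X binomial (Section 16.2.4).

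**Formula.** P(positive | p) = P(X ≥ 18) = Σ C(39, k) p^k (1 − p)^(39 − k), summed over k = 18 to 39. Alpha is this sum at p = 0.33 and power is the sum at p = 0.50.

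**Step 1: try to reproduce the printed figures.**

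| True proportion | Printed | Exact, 18 or more of 39 | Excess of printed value | Exact, 17 or more of 39 |
|---|---|---|---|---|
| 0.33 (alpha) | 0.075 | 0.0600 | 0.015 | 0.1097 |
| 0.35 | 0.16 | 0.0996 | 0.06 | 0.1689 |
| 0.40 | 0.37 | 0.2653 | 0.10 | 0.3807 |
| 0.45 | 0.62 | 0.5042 | 0.12 | 0.6302 |
| 0.50 | 0.82 | 0.7388 | 0.08 | 0.8316 |

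The stated rule gives none of the printed values. Type II error at 0.50 is 1 − 0.7388 = 0.26, against 1 − 0.82 = 0.18 as stated.

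**Step 2: look for another reading.**

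- *Cut-off off by one.* The rule of 17 or more comes close but gives 0.17/0.38/0.63/0.83, not the printed table. Its alpha of 0.110 also exceeds the 0.1 ceiling.
- *Another cut-off at n = 39.* Alpha at 0.33 is 0.184 for 16, 0.110 for 17, 0.060 for 18 and 0.030 for 19. None is 0.075. Of these, 18 is the smallest cut-off that keeps alpha at or below 0.1, so the rule itself is set correctly.
- *Rounding of the null.* A 7.5-month exponential median gives 0.5^(12/7.5) = 0.3299 and alpha 0.0598. A null of 1/3 gives 0.0656. The entries at 0.35 to 0.50 do not depend on the null at all.
- *Over-accrual.* Patients beyond 39 are barred from the decision, so accruing up to 43 adds no power.

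**Step 3: probable origin of the table (an inference).** Take an uncorrected normal approximation at one-sided alpha 0.1:

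- Critical proportion = 0.33 + 1.2816 × √(0.33 × 0.67 / 39) = 0.4265.
- In patients: 39 × 0.4265 = 16.63, a fractional cut-off.
- Power = Φ[(p − 0.4265) / √(p(1 − p)/39)], which is 0.158, 0.368, 0.616 and 0.821 at 0.35, 0.40, 0.45 and 0.50.

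These round to all four printed entries. A real count cannot be cut at 16.63, and the approximation does not explain 0.075.

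**Step 4: what the stated power would require.** With 18 or more of 39, the probability of a positive decision reaches 0.82 at a true proportion of about 0.522, above the plan's 0.50. No cut-off at n = 39 meets both alpha ≤ 0.10 and power ≥ 0.80: 17 fails on alpha and 18 fails on power. The smallest exact design that meets both is 18 or more of 41 (alpha 0.0955, power 0.826).

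**The case against.** The best case on the other side concerns weight, not arithmetic. The test is more conservative than stated on type I error, the rule can run unchanged, and no patient is treated differently. This is a single-arm phase II screening trial in which 18 or more successes only permits a recommendation for further testing. On that view the error is a table to correct.

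The alpha point is indeed the lesser one: 0.060 in place of 0.075 makes a false positive decision less likely, not more. But the primary power claim is 8 points too high at the alternative on which the design rests, and 12 points too high at 0.45. That claim also justifies the choice of 39, so correcting it asks the sponsor whether 74% is acceptable.

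Two other cautions stand. The normal-approximation origin is only an inference, and the finding does not need it. Enlarging the sample is a choice, not a correction. The 41-patient design has little room on alpha (0.1036 if the null is read as 1/3). A rule of 19 or more of 43 also meets both limits (alpha 0.0832, power 0.820) but leaves no reserve under the 43 ceiling. Either change is hard to defend once survival outcomes are visible in a single-arm study.

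**Conclusion.** The concern holds. For the rule as written, attained alpha is 0.060 (stated 0.075) and power at 50% is 73.9% (stated 82%). The table should read 0.10/0.27/0.50/0.74; every printed entry is too high, by 6, 10, 12 and 8 points. The nominal ceiling of 0.1 and the cut-off of 18 are sound.

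The result rests only on the plan's own inputs: 39 evaluable patients, independent binary outcomes at 12 months, a null of 0.33, and no patient beyond the 39th in the decision. It must be fixed because it misstates the error rates of the primary decision, with the harm confined to type II error.

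**What to change.** Keep 18 of 39. In Section 16.2, state a nominal one-sided alpha of 0.1, an attained alpha of 0.060 and power of 74% at a true proportion of 50%. In Section 16.2.4, delete 0.075, give 0.060, and replace the table row with 0.10, 0.27, 0.50 and 0.74. The edits are to wording in two sections and do not alter conduct. The price is a less favourable stated power, which the sponsor should expressly accept.

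Only if the sponsor wants to keep about 82% power, an optional amendment made before outcomes are known could move to 18 or more of 41 evaluable patients. It would change 39 wherever it stands (Sections 16.2, 16.2.1, 16.2.2 and 16.3, the last of which times reporting to "when 39 patients have been followed for at least 12 months"). The current reserve is described in Section 16.2.2: "We anticipate accruing an additional 4 patients to account for ineligibility, cancellation, major treatment violation, or other reasons". It would fall to 43 − 41 = 2, or the ceiling would have to rise to 41 + 4 = 45.

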### 16.2.5 Other Considerations

Adverse events and patterns or failure observed in this study as well as scientific discoveries or changes in standard care will be taken into account in any decision to terminate the study.

## 16.3 Analysis Plan

The analysis for this trial will commence at the time the patients have become evaluable for the primary endpoint (see 16.2). Such decision will be made by the Statistician and Study chair, in accord with the Cancer Center Statistics (CCS) Standard Operating procedures, availability of data for secondary endpoints, and the level of data maturity. It is anticipated that the earliest date in which the results will be make available via a manuscript, abstract, or presentation format is when 39 patients have been followed for at least 12 months.

### 16.3.1 Primary Endpoint:

16.3.1.1 Definition: The primary endpoint of this trial is the proportion of alive (overall survival) at 12 months. Survival time is defined as the time from registration to death due to any cause. All patients meeting eligibility criteria who have signed a consent form and who have begun treatment will be evaluable for the endpoint. All eligible patients will be followed until death or a maximum of 5 years.

16.3.1.2 Estimation: The proportion of successes will be estimated by the number of successes divided by the total number of evaluable patients. Confidence intervals for the

true success proportion will be calculated utilizing Exact Binomial methodology. The distribution of survival time will be estimated using the method of Kaplan-Meier (1958).

16.3.1.3 Over Accrual: If more than the target number of patients are accrued, the additional patients will not be used to evaluate the stopping rule or used in any decision making processes; however, they will be included in final point estimates and confidence limits.

#### 16.3.2 Definitions and Analyses of Secondary Endpoints

16.3.2.1 Progression free survival at 12 months after radiation therapy targeting volumes designed with both F-DOPA-PET and conventional MRI information with historical controls. The target definitions will be similar to those described in section 7.0, Table 1. The progression-free survival at 12 months will be compared to historical controls. The proportion of successes will be estimated by the number of successes divided by the total number of evaluable patients. Confidence intervals for the true success proportion will be calculated utilizing Exact Binomial methodology.

#### 16.3.2.2 Progression Free Survival

The distribution of progression free survival times groups will be estimated using the method of Kaplan-Meier (1958). Time to disease progression is defined as the time from registration to the earliest date documenting disease progression. If a patient dies without documentation of disease progression, the patient will be censored on the last date the tumor was evaluated. If a patient is declared to be a major treatment violation, the patient will be censored on the date the treatment violation was declared to have occurred. In the case of a patient starting treatment and then never returning for any evaluation, the patient will be censored for progression on the last day of therapy.

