### **2.2 Secondary**

2.2.1 Compare progression free survival at 12 months after radiation therapy targeting volumes designed with both F-DOPA-PET and conventional MR image information with historical controls.

2.2.2 Determine acute and late effect toxicity after hypofractionated proton beam radiotherapy treatment including areas of high F-DOPA-PET uptake (T/N>2.0)

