- Clear clinical deterioration not attributable to other causes apart from the tumor (e.g. seizures, medication side effects, complications of therapy, cerebrovascular events, infection, etc.) or changes in corticosteroid dose. The definition of clinical deterioration is left to the discretion of the investigator but it is recommended that a decrease in 20% of KPS or from any baseline to 50% or less be considered, unless attributable to co-morbid events.
- Failure to return for evaluation due to death or deteriorating condition
- Clear progression of non-measurable disease

11.4.1.5 Pseudoprogression (PsP): All of the following must be true:

- Progression of contrast enhancing lesions and or T2-FLAIR is restricted to the initial radiation therapy volume.
- There are no new enhancing lesions outside of the initial radiation therapy volume.
- Patients are stable or improved clinically.
- PsP may be diagnosed at any time during therapy (beyond the typical 12 week window defined by RANO).

	CR	PR	SD	PD 	Preliminary PD/PsP 
T1-Gd +	None	≥50% decrease	<50% decrease- <25% increase	≥25% increase*	Any increase is restricted to initial RT Volume
T2/FLAIR	Stable or decrease	Stable or decrease	Stable or decrease	Increase*	Any increase is restricted to initial RT Volume
New Lesion	None	None	None	Present*	None
Corticosteroids	None	Stable or decrease	Stable or decrease	NA	Stable or decrease
Clinical Status	Stable or improved	Stable or improved	Stable or improved	Worsened*	Stable or improved
Requirement for Response	All	All	All	Any*	All

CR = complete response; PR = partial response; SD = stable disease; PD = progressive disease, PsP = Pseudoprogression

NA - Increase in corticosteroids alone will not be taken into account in determining progression in the absence of persistent clinical deterioration

1. RANO Progression occurs when any of the criteria with \* are present.
2. Confirmed PD requires all of the following if not all criteria are met then Preliminary PD
  - More than 3 months post RT
  - Radiologic progression by central review [REDACTED] by RANO criteria
  - Clinical progression as determined by treating Oncologist
  - Cannot be considered Pseudoprogression
3. Patients with possible PsP should initially be given the Objective Status of Preliminary Progression. Once PsP or Progression is confirmed, the Objective Status can be changed accordingly.

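### Section 16.3.2.2 is labelled progression-free survival but censors deaths without documented progression, and 16.3.2.1 does not define a 12-month PFS success

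*Combined protocol and SAP*

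**What the plan says.** - Section 2.2.1 sets the secondary goal: "Compare progression free survival at 12 months after radiation therapy targeting volumes designed with both" PET and MR information, against historical controls.
- Section 16.3.2.1 repeats the comparison ("The progression-free survival at 12 months will be compared to historical controls") and gives the estimator: "The proportion of successes will be estimated by the number of successes divided by the total number of evaluable patients", with an exact binomial interval. It does not say what a PFS success is. The only success defined in Section 16 belongs to overall survival (16.2): "A patients will be considered a success if they are alive at 12 months".
- Section 16.3.2.2, headed Progression Free Survival, applies Kaplan-Meier to PFS times. Its only time variable is this: "Time to disease progression is defined as the time from registration to the earliest date documenting disease progression". Two of its censoring rules matter here. For deaths: "If a patient dies without documentation of disease progression, the patient will be censored on the last date the tumor was evaluated". For a patient who starts treatment and is not seen again: "never returning for any evaluation, the patient will be censored for progression on the last day of therapy".
- Section 11.4.1.4 includes this among the criteria for progression: "Failure to return for evaluation due to death or deteriorating condition".

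**The concern.** PFS counts death from any cause as an event. Section 16.3.2.2 removes such deaths from the risk set and, by backdating to the last scan, removes them before they happen. The result is a time-to-progression curve under a PFS label. In elderly glioblastoma, death is unlikely to be independent of progression, so it is poor grounds for censoring. Even if it were independent, the curve would describe progression in a setting where nobody dies first, which is not the stated goal.

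As an estimate of PFS the curve is expected to be too high, to the extent that such deaths occur. That would favour the regimen against any historical series that counts death as an event. The proportion in 16.3.2.1, on its natural reading, counts the same deaths as failures. One dataset could then yield two different 12-month PFS figures, each consistent with the plan.

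**Working it through.** The plan states no PFS rate, control rate or event count, so there is no figure to reproduce. The check has two parts.

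**1. The text side by side**

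| Situation | 16.3.2.2 | 11.4.1.4 | 16.3.2.1 |
|---|---|---|---|
| Death, no documented progression | Censored at last tumor evaluation | Progression, if the death is why the patient did not return | Not stated; failure on the natural reading |
| Never returns after starting treatment | Censored on last day of therapy | Progression, if due to death or deterioration | Not stated |

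No section defines PFS as progression or death. For overall survival, 16.3.1.1 does give a full definition, from registration to death from any cause.

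**2. Illustrative size**

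Inputs:
- Median PFS of 4.2 months, from the randomized comparison of two short radiation schedules cited in the Background. Times are assumed exponential, so S(t) = 0.5^(t/4.2). This gives S(2) = 0.719, S(8) = 0.267, S(12) = 0.138 and S(14) = 0.099.
- s, the share of PFS events that are deaths without documented progression. The documents give none; 0%, 10%, 20% and 30% are assumed.
- Scans every 2 months during Cycles 2-7 (Section 4.0, note 7), then visits at the clinician's discretion (note 1). By Section 7.3, the time from start of radiation to the end of Cycle 7 is 1-2 weeks, plus one month, plus six 28-day cycles (168 days, about 5.5 months), or about 6.8-7.0 months. With an assumed interval from registration to radiation, this is taken as month 8. Scans are counted from registration, and progressions are placed at their true times.

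Formulas for the 12-month Kaplan-Meier value, with k = 1 - s(1 - 0.719):
- A, censored at death: S(12)^(1-s)
- B, censored at last scan, scans 2-monthly to month 12: S(12)/k^6
- C, scans to month 8, next at month 14: [S(8)/k^4] x [(1-s)S(12) + s S(14)] / [(1-s)S(8) + s S(14)]
- D, scans to month 8, none later: S(12)/k^4

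For s = 20%, k = 1 - 0.2 x 0.281 = 0.944. Then A = 0.138^0.8 = 20.5%, B = 0.138/0.944^6 = 19.5% and D = 0.138/0.944^4 = 17.4%.

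| s | True PFS | A | B | C | D |
|---|---|---|---|---|---|
| 0% | 13.8% | 13.8% | 13.8% | 13.8% | 13.8% |
| 10% | 13.8% | 16.8% | 16.4% | 16.0% | 15.5% |
| 20% | 13.8% | 20.5% | 19.5% | 18.8% | 17.4% |
| 30% | 13.8% | 25.0% | 23.4% | 22.2% | 19.6% |

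A simulation of 2,000,000 patients agrees to within 0.1 point. Under backdating as written (B to D), the excess over 13.8% is 1.7-2.6, 3.6-5.7 and 5.8-9.6 points for s = 10%, 20% and 30%.

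The number of the 39 patients dying without documented progression by month 12 is 39 x s x (1 - 0.138) = 3.4, 6.7 or 10.1. For scale, 5 successes in 39 has an exact 95% interval of 4.3% to 27.4%.

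The effect does not hinge on the 4.2-month median. By formula A with s from 10% to 30%, an assumed median of 6.0 months moves 25.0% to 28.7-37.9%, and 7.5 months moves 33.0% to 36.9-46.0%.

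**The case against.** The strongest reply is that the goal is a 12-month rate, that 16.3.2.1 estimates it as a simple proportion, and that 16.3.2.2 only describes a distribution without naming a 12-month reading or a test. The phrase progression-free survival also has an obvious meaning, so the missing success definition is a matter of tidiness. This has some force: on the natural reading, the 16.3.2.1 estimate is not biased. But a curve published under the PFS heading will be read at 12 months, and it is mislabelled whatever its use.

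The natural reading is also not secured by the text. If only documented progression were a failure, the proportion would be 1 - (1-s)(1 - 0.138) = 22%, 31% or 40% for s = 10%, 20% or 30%. That lies above the Kaplan-Meier values, so the gap would change sign. This argues for stating the definition.

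Second, 11.4.1.4 may leave few deaths to censor. That is true if it governs, but 16.3.2.2 expressly censors them, so the two sections conflict and one does not repair the other.

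Third, the illustration is soft. The share s has no source, and the 4.2-month median comes from a comparison of radiation schedules, whereas this trial adds temozolomide. Scenarios C and D place progressions at their true times although no scan would document them, and Section 13.3 foresees continued clinically indicated MRI. These limits stand. The lower ends of the ranges are not firm floors, and the figures show direction and scale only.

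**Conclusion.** The concern holds. Followed as written, 16.3.2.2 produces a time-to-progression curve labelled PFS. It conflicts with 11.4.1.4, and 16.3.2.1 leaves a PFS success undefined. None of this depends on an assumption.

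The size does. With exponential times, a 4.2-month median and 10-30% of PFS events being deaths without documented progression, the 12-month Kaplan-Meier figure exceeds true PFS by about 2 to 10 points under backdating. The excess tends to zero if few such deaths occur or if 11.4.1.4 governs. It lies within sampling error for 39 patients, but it is systematic, so the confidence interval does not account for it.

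This is a secondary endpoint with no stated threshold, and the primary 12-month survival decision is unaffected. It should be corrected before the analysis, so that the choice of rule is not made with the data in view.

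**What to change.** 1. In 16.3.2.2, define PFS as the time from registration to the first of documented progression or death from any cause, and delete the rule that censors deaths.
2. In 16.3.2.1, state that success means alive and progression-free at 12 months from registration, so that death before 12 months is a failure. Say how patients who cannot be assessed at 12 months are classified.
3. Reconcile the censoring rules in 16.3.2.2 with 11.4.1.4. Once death is an event, what remains is mainly non-return because of deterioration and the date assigned to it. State also whether preliminary or confirmed progression, as distinguished in 11.4.1, counts as documented.
4. If the present variable is wanted, report it separately as time to progression.

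The cost is wording in 16.3.2.1 and 16.3.2.2, with a cross-reference or small edit in Section 11 if the reconciliation calls for one. Death dates are already collected for the primary endpoint. The PFS estimate may be less favourable if such deaths occur.
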